## **2.2 STUDY SITES**

This study will be conducted in Ethiopia and in Nigeria. It will constitute an intervention and a comparison group. In Nigeria the study will be conducted in two states i.e., Kaduna and Jigawa. For the intervention group, the study will be conducted in the specific LGAs where the MMA program enhanced with the MNCH component is implemented. For the comparison group, the study will be conducted in LGAs implementing MMA without the MNCH component. At the LGAs, the study will be conducted in specific PHCs which have been purposely selected to host the evaluation and the catchment areas that are served by the PHCs.

In Ethiopia, the study will be implemented in four out of the five regions that implement the Smart Start interventions (avoiding the South Western region which started implementing Smart Start in 2023). Specifically, the intervention group will be based in nine (9) woredas in the four regions where Smart Start with Smart pathways is implemented. The comparison group will be based in 8 woredas geographically distant from those offering Smart pathways but offering Smart Start. In Ethiopia, the evaluation will be conducted in health centres and health posts that offer comprehensive ANC services.

For both Nigeria and Ethiopia, comparison areas will be locations implementing the current MMA or Smart Start intervention without the MNCH component. These will be carefully selected to ensure they match the intervention locations in terms of the demographics of married adolescent girls and based on the economic and health indices. Because of comparing the intervention outcomes against the current package of interventions, this study will ideally be measuring the incremental effectiveness of the expanded interventions and not with a counterfactual (as would have been if the comparison was done against routine government-led MNCH components).

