## **SUMMARY**

### **CONTEXT**

Population Services International, Inc. ("PSI") implements A360 Amplify in Nigeria, Kenya, and Ethiopia. A360 Amplify has developed innovative and unique interventions for each geography to support adolescent girls to access voluntary modern contraception according to their needs and preferences. As part of the current project phase, A360 completed the design of a maternal, neonatal and child health (MNCH) component in 2023 that will be layered on Matasa Matan Arewa (MMA) in Nigeria and Smart Start interventions in Ethiopia. The intervention components will target married adolescent girls 15-19 in both countries with an expansion to include 20-24 years old in Ethiopia. There is paucity of evidence on the effectiveness of upstream interventions at creation demand and access to antenatal care (ANC) among adolescent girls and young women (AGYW) from the regions where A360 operates. Consequently, parallel to the implementation of these two components, A360 has designed an evaluation to determine the effectiveness of these components in improving the comprehensive knowledge of what is needed to pursue healthy pregnancies, increase girls' self-efficacy to access ANC and increase support from their key influencers to pursuing healthy pregnancies.

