The proposed additional participants will be drawn from the same woredas where participants were initially recruited, though new but from adjacent kebeles might be required in case adequate sample is not generated from the recruitment from the initial kebeles. An exception to the woredas is Tehuldere in Amhara where we have selected a complementary intervention woreda (Nineth) because after attempting to recruit participants from multiple kebeles, the recruitment yield was extremely low. Anecdotal reports suggest that there are existing MNCH programs in the woreda

which have been supporting women to adopt contraceptives and MNCH interventions. Since our eligibility criteria is AGYW who are not using a contraceptive method and who have not started ANC, this implies that it might not be feasible to recruit the desired sample from the same woreda even after exhaustively recruiting participants from all kebeles in the woreda. The total sample size for the survey therefore increases from 2,180 participants to 2,420 participants – 1,090 in Nigeria and 1,330 in Ethiopia. These numerical adjustments only affect the excess sample for non-pregnant girls since sample for pregnant girls that had been projected is preserved – we are topping up to maintain the earlier projection. In both countries, participants in the comparison arm will receive services as is expected based on the Ministry of Health guidelines in Ethiopia and Nigeria. Therefore, this group will be a partial control group.

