#### **Smart Pathways**

This component is layered on Smart Start. Smart Start targets married adolescent girls 15-19 and their spouses in Ethiopia in five regions: Oromia, Amhara, SNNPR, Sidama and South Western. Smart Start is implemented as part of the national Health Extension Program (HEP) through health

posts. Using a Smart Start discussion guide called a 'goal card' health extension workers (HEWs) engage married adolescent girls alone or with their husbands to discuss how the use of modern contraceptive methods to plan their families can facilitate financial planning and enhance the financial security of their families. This seamlessly creates relevance of contraceptives within a context where a direct conversation on modern contraceptives would be difficult. Smart Pathways (the MNCH component) is an expansion of Smart Start. Unlike Smart Start, it targets AGYW 15-24. In the communities, a team of trained FMOH-recognized community mobilizers consisting of members of the women development army (WDA) and Smart Start Navigators (SSNs) approach married adolescent girls from their communities and introduce them to Smart Start. Married girls who express interest to take up birth spacing are linked to HEWs who are working in the community or at health posts to receive the Smart Start intervention (pathway 1).

For girls who are ambivalent to receiving contraceptive counselling and services or those who intend to conceive soon, the trained mobilizers link them to an HEW who takes them through the Smart Pathways component for non- pregnant girls. When they land at the HEW, the HEW uses the Smart Pathways guide to discuss issues related to Preconception Care Counselling and early ANC initiation (pathway 2). For girls who have missed their periods or suspect that they are pregnant, the trained mobilizers link them to health centres or health posts where HEWs or midwives take them through a seven-step process that covers pregnancy testing, building demand for ANC, the benefits and components of ANC, danger signs of pregnancy, smart nutrition, preparation for delivery and post-partum family planning (pathway 3). Girls in Pathway 2 who conceive are referred to navigate through pathway 3 when that time comes. The three pathways are illustrated in Figure 1.

As married pregnant AGYW navigate through ANC, they are offered services based on the Ethiopia Federal Ministry of Health antenatal care guidelines (Ministry of Health of Ethiopia, 2022).

[figure not shown]

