## 1.4 JUSTIFICATION FOR THE RESEARCH

Ethiopia and Nigeria have poor MNCH indicators particularly regarding to adolescents, although older women are not spared either. According to Ethiopia Mini Demographic Health Survey (EMDHS) of 2019, among women 15-49 years old who had a live birth in the five years preceding the survey, 74% had at least one ANC visit and only 43% attended four or more ANC visits. The rates of ANC attendance were lower among women under 20 years (Ethiopian Public Health Institute & ICF, 2019). Earlier in the 2015 EDHS, the median age at first ANC visit was 4.7 months and only 20% of women had started ANC by the gestational age of 20 weeks. In that same survey, among women 15-49 years who had a live birth in the past five years, 45% were informed of danger signs or pregnancy complications during ANC visit, 56% were informed about birth preparedness and 11% were informed of the place of birth during ANC. Four in five women 15-49 years who had birth in two years before survey did not have a postnatal check-up within 48 hours of delivery(CSA and ICF, 2016).

In Ethiopia, early marriage is common since 17% of adolescent girls aged are married. Teen marriage increases to 60% among 20-24-year-old women. Among currently married girls 15-19 years, 42% have at least 1 living child. Among girls 15-19 who had a live birth or pregnant at time of survey, 13% had started childbearing, 10% had birth, and 2% were pregnant. In the 2015 EDHS,

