## **3.7 CONFIDENTIALITY AND PRIVACY**

Protecting research participants' privacy is a major goal for this study. Field research teams will be trained on study procedures and research ethics to ensure they are sensitized to risks and respect of privacy. As previously described, all identifying information needed for the recruitment

of study participants, whether adults or AGYW, will be destroyed at the completion of data collection. No identifying information will be collected during individual or group discussions.

All the data from the field will be thoroughly reviewed for identifying information and all these stripped off – personal names, phone numbers or addresses. The Investigators will instead devise a coding scheme to indicate their sex, age group for AGYW (18-19 or 20-24), and standing in the community (health provider, mobilizer, husband), and geographic region. This coding scheme will be applied to data outputs before data analysis. Any quotes used in study outputs or shared publicly will use this coding scheme (sex, age/community standing, geography) exclusively.

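### In Ethiopia the comparison package is aimed at ages 15-19 but the survey enrols 15-24, so the unqualified claim to measure the increment over the current package is not supported for women aged 20-24

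*Protocol*

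**What the plan says.** Section 2.2 places the comparison group in areas that run MMA or Smart Start without the new component. It concludes that "this study will ideally be measuring the incremental effectiveness of the expanded interventions and not with a counterfactual", and explains that a contrast with routine government services is not what is being made. Section 2.11 repeats this: the revamped programmes are set against the current package, and a comparator of unsupported government facilities would have been ideal but might not be feasible.

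Section 1.3 (Smart Pathways) gives the ages. For the current package: "Smart Start targets married adolescent girls 15-19 and their spouses in Ethiopia in five regions". For the expanded package: "Unlike Smart Start, it targets AGYW 15-24". The Summary (Context) also ties the older band to the new component, "with an expansion to include 20-24 years old in Ethiopia".

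Section 2.3 and Table 1 set survey eligibility at 15-24 in Ethiopia and 15-19 in Nigeria, with no difference between arms. Section 2.9.1 describes one two-group comparison of slopes, with no age band. The Summary (Methods) describes the comparator in other terms: "participants in the comparison arm will receive services as is expected based on the Ministry of Health guidelines in Ethiopia and Nigeria". It calls that group a partial control.

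**The concern.** The stated aim is to isolate what the new component adds to a programme that is already running. That reading requires the running programme to be directed at the same women in both arms. In Ethiopia this is true of ages 15-19. For ages 20-24 it is not, on the protocol's own description: in intervention woredas they are offered a package newly opened to their age group, and in comparison woredas the existing package is not aimed at them. Their contrast may lie closer to new programme versus routine services, which is the contrast that Section 2.2 says the study does not make.

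At stake is what the Ethiopian result can be said to show. A favourable pooled estimate would be reported as the added value of the maternal and newborn layer, although part of it could come from bringing an untargeted age group into the programme. Nigeria enrols only 15-19, so the two country estimates would also not answer the same question if they were set side by side.

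**Working it through.** **The passages compared, Ethiopia**

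| | Ages 15-19 | Ages 20-24 |
|---|---|---|
| Enrolled in both arms (Section 2.3, Table 1) | yes | yes |
| Targeted by Smart Start (Section 1.3) | yes | no |
| Targeted by Smart Pathways (Section 1.3) | yes | yes |
| Contrast that follows | expanded versus current package | expanded package versus no current package aimed at them |

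The label in Section 2.2 fits the first column only. Section 2.9.1 does not separate the columns, and Section 2.11 does not list the mismatch among the limitations. Site matching in Section 2.2 refers to the demographics of married adolescent girls and does not mention the older band.

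**The plan's sample size, reproduced.** Inputs from Section 2.6: proportions 0.30 and 0.40, no change in the comparison group, 80% power, two-sided 5%, design effect 1.2, 10% non-response, then 10% attrition. The within-person correlation is not given in the text available; I assume 0.5.

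- Variance of the logit change, intervention: 4.762 + 4.167 − 2 × 0.5 × √(4.762 × 4.167) = 4.474.
- Variance of the logit change, comparison: 2 × 4.762 × (1 − 0.5) = 4.762.
- Effect: logit 0.40 − logit 0.30 = 0.4418; squared, 0.1952.
- n per arm = (1.960 + 0.8416)² × (4.474 + 4.762) / 0.1952 = 371.3.
- Total = 2 × 371.3 × 1.2 / 0.9 = 990, against the stated 991. Then 991 × 1.10 = 1,090, or 545 per arm.

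The stated size is reproducible and is not in dispute. It shows that the trial is built around a 10-point effect.

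**How mixing works.** Let q be the share aged 20-24:

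pooled effect = (1 − q) × effect at 15-19 + q × effect at 20-24.

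The pooled effect equals the effect at 15-19 only if q = 0 or the two effects are equal. The protocol gives neither q nor age-specific effects, so every value below is assumed.

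| q | 15-19: 10 points; 20-24: 15 to 20 points | 15-19: 0; 20-24: 20 points |
|---|---|---|
| 0.2 | 11 to 12 | 4 |
| 0.5 | 12.5 to 15 | 10 |
| 0.8 | 14 to 18 | 16 |

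**Precision of a 15-19 estimate on its own.** Approximation: follow-up comparison of 0.30 with 0.40, effective n per arm = 545 × (1 − q) × 0.9 × 0.9 / 1.2.

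| q | Enrolled per arm, 15-19 | Effective n | Power |
|---|---|---|---|
| 0 | 545 | 368 | 81% |
| 0.2 | 436 | 294 | 72% |
| 0.5 | 272 | 184 | 52% |
| 0.8 | 109 | 74 | 24% |

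Starting instead from the 661 that Table 2 now gives for the Ethiopian intervention arm, q = 0.5 leaves 330 per arm, effective n 223, and power of about 60%.

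**The case against.** The strongest reply is that the two contrasts may be close in practice. Smart Start is described as family-planning counselling framed around household finances. Survey participants are pregnant (70% planned) or not using contraception, and the primary outcome is knowledge of preconception care, which Smart Start is not described as teaching. For many girls aged 15-19, too, the working contrast may be the new content against none. This stands: it limits how large the distortion is likely to be and makes it an open question rather than an established bias. It does not make the label in Section 2.2 correct for ages 20-24.

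Second, the comparator is set by place, and the wider age reach can be seen as part of what is being added. That is a coherent estimand, but not the one Section 2.2 words, and Section 2.11 does not supply it.

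Third, age strata and interaction terms are commonly left to the analysis plan, which is not shown. Their absence is not the fault raised here. The fault is the unqualified comparator statement in the protocol itself.

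A reader might also infer more than the text supports:

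- That Smart Start serves only ages 15-19. The protocol says that it targets them; it does not say that older women are turned away.
- That the Summary proves women aged 20-24 in the comparison arm get routine care alone. Its sentence covers all comparison participants in both countries, at every age.
- That most of the Ethiopian sample is 20-24, from the marriage percentages in Section 1.4. Those are not the enrolled mix, and the pregnancy and contraception criteria shift it by an unknown amount.
- That the age code in Section 3.7 shows the survey cannot separate the bands. That code serves de-identification and the labelling of quotes; eligibility already requires age.

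**Conclusion.** The point holds in a limited form. On the protocol's own description, the claim to measure the increment over the current package is not supported for Ethiopian women aged 20-24, and the pooled Ethiopian estimate may combine two contrasts. The conclusion rests on reading the stated target ages as describing whom the programmes reach; the wording that sets Smart Pathways apart from Smart Start supports that reading but does not settle actual reach.

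The size of any distortion cannot be computed. The pooled figures above are illustrations under assumed shares and effects. They show only that, if effects differ by age, a null increment at 15-19 could appear as a pooled effect of the order the trial is designed to detect.

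It would go too far to say that the pooled Ethiopian result is uninterpretable or should be replaced. It can be read as the expanded programme, including its extension to 20-24, against Smart Start areas. The point concerns Ethiopia only, because Nigeria's enrolment and its programme as described both cover 15-19. It should be corrected, since it decides what the trial may conclude.

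**What to change.** 1. Reconcile the Summary (Methods) with Sections 1.3, 2.2 and 2.11, and state the Ethiopian comparator separately for 15-19 and 20-24, including whether women aged 20-24 in comparison woredas are offered Smart Start.
2. Keep the pooled Ethiopian estimate as primary, and label it as the expanded programme, with its extension to 20-24, versus Smart Start areas.
3. In Section 2.9.1, or by reference to the analysis plan, report 15-19 and 20-24 estimates beside the pooled one, with an age-band by group-by-time term.
4. Base any statement about the increment over Smart Start, and any comparison with Nigeria should one be made, on the 15-19 estimate.
5. Add the age mismatch to Section 2.11.

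The cost is wording, one model term and two stratum estimates, using age already needed for eligibility. The downside is a narrower incremental claim resting on an imprecise estimate: about 52% power for 10 points if half the sample is 20-24 (an assumed share) and 545 per arm are counted, or about 60% from the enlarged Ethiopian sample. That loss is why the 15-19 result should stand beside the pooled one and not replace it.

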## **2.3 STUDY PARTICIPANT GROUPS**

The primary target group for this study will be **married AGYW aged 15-19 years from the two states in Nigeria and 15-24 years who reside in four regions in Ethiopia**. Given that this study explores the experiences of AGYW related to planning for pregnancy and experiencing pregnancy, birth and the postpartum periods, the study will work to recruit a mix of married AGYW who have both experienced a prior pregnancy and those who have not (but at risk of pregnancy).

The secondary target groups for this study will include:

- i. Male partners (husbands) of married AGYW who have received the MNCH intervention in Nigeria
- ii. Health providers and community health mobilizers from the intervention locations

All husbands, health providers and community mobilizers will be over the age of 18 years. The inclusion and exclusion criteria for all groups are provided in Table 1.

**Table 1: Inclusion and exclusion criteria**

Group	Inclusion	Exclusion
Married AGYW (survey)	
 
• Aged 15 to 19 (Nigeria) and 15-24 (Ethiopia)
 
• Married
 
• Resident in a study site
 
• If pregnant should be at most 24 weeks gestation
 
• If not pregnant, at risk of pregnancy (not using a contraceptive method at the time of the survey with or without intend to conceive)
 
• Consent to participate in the study
 
	
 
• Married AGYW, aged 15-19 (Nigeria) or 15-24 (Ethiopia) who decline to give consent
 
• If pregnant, has an advanced pregnancy (<math>\geq</math> 25 weeks gestation)
 
• If not pregnant, currently using a contraceptive method
 

Married AGYW (FGDs and IDIs)	
 
• Married and aged 15 to 19 (Nigeria) and 15-24 (Ethiopia)
 
• Currently pregnant or in the post-partum period (after recent delivery)
 
• Participated in the full MNCH components of MMA or Smart Start
 
• Consent to participate in the study
 
	
 
• Married AGYW aged under 15 or over 19 (Nigeria) or over 24 (Ethiopia)
 
• Not pregnant or not in post-partum period
 
• Did not participate in MNCH component
 
• Decline to consent
 

Husbands of AGYW (Nigeria only)	
 
• Male aged 18 years and over
 
• Husband of an AGYW aged 15 to 19
 
• Has participated in husband sessions (at the community or facility) of the MNCH component
 
• Consent to participate in the study
 
	
 
• Males under 18 years
 
• Did not participate in the husband sessions for the MNCH component
 
• Husband who decline to give consent
 

Health worker / community health mobilizer	
 
• Employed as a health worker (can be nurse, midwife, etc.) or mobilizer (female mentor, member of WDA or MIPCA) within the study site.
 
• Served at the facility or community for this role for six or more months.
 
• Provides services along the MNCH continuum of care (e.g., ANC, delivery, PPFP, etc.)
 
	
 
• Recently employed health worker or mobiliser (< 6 months)
 
• Not familiar with MNCH or FP services
 
• Unwilling to consent
 

## 2.4 PARTICIPANT RECRUITMENT

The following section outlines how each group will be recruited to participate. The recruiters' role will be to invite potential participants to the evaluation, briefly assess eligibility and to seek their

permission to share their contact details with the research team. They will be guided by a recruitment script (see Appendices A-F) so that the procedure is standardized. The recruitment procedures for each study group are detailed in the sub-sections below.

#### 2.4.1 Recruitment of married AGYW

Different recruitment procedures will be used for the Quantitative survey and the Qualitative component.

**(i) For the quantitative survey** in both Nigeria and Ethiopia, the research team will leverage already existing trained mobilizers (female mentors in Nigeria & members of WDA and female SSNs) to perform recruitment procedures. The mobilizers will be trained to identify and recruit AGYW from the community guided by a recruitment script. The mobilizers in Nigeria and Ethiopia are familiar with their communities and will approach potential participants directly by face-to-face contact during their routine household visits, in clinics and/or during community gatherings.

When a mobilizer approaches a married AGYW, she will ask her for verbal consent to speak to her in private. She will ask her the four screening questions (in the recruitment script) after providing brief details about the nature of the evaluation. If the potential participant is eligible and has expressed interest to participate, the mobilizer will obtain the contact details (name, phone number and details of residential address) and record these in a recruitment confidential contacts' list (**Appendix Q attached to the submission**). Details of residential address are collected because a substantive number of AGYW in these locations might not own or have access to a phone as reported in recent surveys – 40.2% in Ethiopia and 6-21% in northern Nigeria (Krug et al., 2021a, 2021b). These lists will be passed to a data collector (research assistant) working in the study locality on a daily basis. The AGYW will also be notified that they should expect a call or a visit from a female enumerator at a future date. During the period when we execute a modification to increase the number of pregnant girls in Amhara, South, and Central Ethiopia and Sidama, recruiters will only identify, approach and invite pregnant girls only. To do so, they will be trained not to field the screening question on contraceptive use (question 3) in the recruitment script - the rest of the procedures and questions will be fielded as they are. During this period, they will only capture contact details of eligible pregnant girls in the confidential recruitment contact lists.

Trained enumerators will employ these lists to contact potential participants to provide more information about the study guided by the information sheets (attached to the submission) and to set an appointment date for the interview (if contact is on phone). If the AGYW listed does not have a phone contact, the call is unanswered or the call doesn't go through, the data collector will arrange to pay a physical visit to the AGYW's residence to make an in-person contact. Upon arrival at the residence, the data collector will introduce herself and request to speak to the AGYW, without directly disclosing reproductive health. During the visit, the data collector will offer brief information about the study. If the AGYW is willing and available for the interview at that time, she will continue and perform consenting procedures then conduct the interview if consent is granted. This will make it convenient for the participant and the study.

However, if the AGYW is unavailable for the interview on during that visit date and time, an appointment will be scheduled.

For the AGYW with an appointment, on the date of the scheduled interview the research team will provide detailed information and obtain informed consent form. Thereafter, the data collector will perform the interview. For recruitment in the Oromia region only, enumerators will be assigned quotas (numbers of pregnant versus non-pregnant girls) to survey from a health post. As they continue to consent participants and perform interviews, they will keenly monitor these numbers. Once they had reached the allocated sample for a particular group (in most cases it will be non-pregnant girls), thereafter they will confirm the pregnancy status of the AGYW remaining on the list when contacting them (using the information sheet approved) and if an AGYW is not pregnant, they will let them know that the sample has been reached and that they will not be included in the study going forward but appreciate them for their interest to join the study. They will not invite these AGYW for in-person contact. This will prevent AGYW from spending time and effort travelling to the facility when they will not be recruited. If an AGYW is confirmed to be pregnant, the study procedures will continue as described earlier. The personal identifying information (PII) collected during recruitment will be destroyed under the instruction of the PI following the completion of recruitment and will not be recorded alongside any data collected in this activity.

**(ii) For the qualitative component**, AGYW will be recruited primarily through Smart Start and MMA program staff, particularly health extension workers and health providers working at the facilities implementing the MNCH component. The recruiters will be provided with guidance on who should be recruited for FGDs and IDIs. They will identify AGYW from the service delivery records which are used to document the attendance of AGYW to MNCH sessions. They will use the instructions provided by the study team to purposely sample enough potential participants from the client records. Only AGYW who have phone numbers indicated in the client records will be selected. This is because tracing AGYW who do not have documented phone contacts will be impossible since detailed physical addresses are not routinely collected by providers. Furthermore, the communication of the scheduled date, time and venue for the IDIs and FGDs will be impossible without phone contacts.

Using the recruitment script, recruiters will contact the identified AGYW through the phone contacts documented in the program records. During the phone call, once the recruiters have introduced themselves and obtained verbal consent, they will ask the potential participants if that is a good time to speak. They will also request the AGYW to identify a secluded place that offers privacy and then provide a brief description of the evaluation. This will ensure that no one could hear what is being communicated during the phone call. Thereafter, they will field the screening questions to determine eligibility and then proceed to gather contact details which will be documented immediately on the confidential contact lists.

Once recruitment is completed, the contact information will be compiled together and transferred to the lead investigators for each country. The investigator will then coordinate so that the qualitative researcher in the team contacts the participant by phone to complete the recruitment procedures. The qualitative researcher will then schedule an appointment and

venue for the IDI or FGDs. On the scheduled date of the FGD or IDI, full consenting procedures will be executed. Similar to the quantitative survey, all PII details will be destroyed by the PI once recruitment is completed.

